## 8.5 Statistical Analysis

### 8.5.1 Methods of Analysis

Summaries for continuous variables will include the sample size, mean, SD, median, minimum, and maximum. Minimums and maximums will be reported with the same precision as the raw values; medians and means will have 1 more decimal place; SD will have 2 more decimal places. Summaries for discrete variables will include the tabulation of frequencies and percentages. Differences between treatment groups will be calculated as LE gel 0.38% minus vehicle, and change from baseline will be calculated as follow-up visit minus baseline. The baseline visit will be defined as Visit 3 (Postoperative Day 1). For IOP, change from the previous visit will also be summarized.

#### 8.5.1.1 Efficacy Endpoint Analyses

##### Analysis of Primary Efficacy Endpoints

The primary efficacy endpoints are the proportion of subjects with complete resolution of AC cells at Visit 5 (Postoperative Day 8) and the proportion of subjects with Grade 0 pain at Visit 5 (Postoperative Day 8). Primary efficacy analyses will be based on the intent-to-treat (ITT)

population with missing data imputed as failures (subjects placed on rescue medication prior to the visit being summarized will also be considered failures).

The primary efficacy analyses of the difference between each active treatment group and the combined vehicle treatment group at (Visit 5) Postoperative Day 8 will be tested using Pearson Chi-squared tests with p-values adjusted using a Bonferroni-based tree gatekeeping strategy with the structure shown in Table 3. Null hypotheses with adjusted p-values  $\leq 0.05$  will be rejected.

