### Visit 3 (Postoperative Day 1) Criteria

9. Have undergone routine, uncomplicated cataract surgery (phaco-emulsification with posterior chamber IOL implantation, not combined with any other surgery) in the study eye.
10. For female subjects, **either**
  - Not be of childbearing potential (female subjects not of childbearing potential must be postmenopausal at least 12 months prior to Visit 3 or permanently sterilized [eg, tubal occlusion, hysterectomy, bilateral salpingectomy])
  - or**
  - Have a negative urine pregnancy test result at Visit 3 (Postoperative Day 1).
11. Continue to meet all requirements of Inclusion Criterion #7.
12. Have  $\geq$  Grade 2 anterior chamber (AC) cells (6-15 cells) in the study eye.

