6.1.3 Visit 3: Postoperative Day 1 (Randomization [18 to 34 hours post-surgery])

**NOTE:** *Post-surgery visits should be scheduled so that IOP can be assessed within  $\pm$  2 hours of the time of IOP assessment on Visit 1.*

- Perform a urine pregnancy test, as applicable
- Perform a clinical assessment of ocular symptoms
- Perform assessment of pin-holed Snellen VA
- Perform biomicroscopy assessments
  - Assess AC cells (refer to [Appendix B](#))
    - If the AC cell grade is  $\geq$  2, then the subject is eligible and will be randomized.
    - If the AC cell grade is  $<$  2, then the subject is not eligible and will be a screen failure.
- Perform IOP measurement
  - IOP should be assessed within  $\pm$  2 hours of the time IOP was assessed at Visit 1 (Screening). Measurement of IOP must occur after the assessment of ocular symptoms and biomicroscopy.
  - If a one-time intervention is necessary to reduce IOP prior to randomization (eg, 'burping' the paracentesis, Diamox, or topical hypotensive agent) and the pressure returns to normal, the subject can be randomized into the study. The AE and intervention should be recorded on the appropriate logs (eg, Adverse Event, Concomitant Medication, and Ocular Surgical Intervention) and the final IOP measured prior to randomization should be recorded in the eCRF.
- Randomize eligible subjects by assigning the next applicable subject kit number
- Dispense study drug kit to the subject

- Instruct the subject to instill 1 drop of study drug into the study eye according to the instructions provided with the kit.
  - Subjects should instill their initial dose while in the clinic to ensure that they understand and are able to follow instructions for instillation.
  - The Investigator and study staff involved in assessments of safety and efficacy must not be present during the in-office study drug instillation.
  - Remind subjects to instill all doses on Day 1 even if the interval between doses is shorter than described in the kit instructions.
  - For those subjects receiving a topical antibiotic, remind the subject that the topical antibiotic drops must be instilled a minimum of 15 minutes BEFORE study drug application.
- Collect and record AEs and changes in concomitant medications

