### 8.3 Sample Size

Approximately 588 subjects will be randomized in a 2:2:1:1 ratio to LE gel 0.38% dosed TID, LE gel 0.38% dosed BID, vehicle dosed TID, and vehicle dosed BID.

The 2 vehicle arms will be combined into 1 treatment group in the statistical analysis, and hence the study will have 3 treatment groups, ie, LE gel 0.38% dosed TID, LE gel 0.38% dosed BID, and (combined) vehicle group. Each of the three treatment groups will consist of approximately 196 subjects.

Estimates of efficacy used to calculate the sample size were based on the integrated database of 4 previous similar studies. Two of these studies were conducted with LE gel, 0.5% and vehicle, each dosed QID. One study was conducted with LE gel, 0.38%, dosed TID and BID. One study was conducted with LE gel, 0.38%, dosed BID.

Powers and sample sizes for individual comparisons were estimated using nQuery Advisor® 7.0 (Janet D. Elashoff, Copyright 1995-2007). Power to detect one or more differences and both differences was estimated by computer simulations of 250,000 trials.

#### 8.3.1 Complete Resolution of AC cells in the Study Eye at Visit 5

A two group  $\chi^2$  test with a 0.025 two-sided significance level will have 87% power to detect the difference between a LE gel 0.38% proportion,  $\pi_1$ , of 0.283 and a vehicle proportion,  $\pi_2$ , of 0.143 (odds ratio of 0.423) when the sample size in each group is 196. The two simultaneous  $\chi^2$  tests (TID and BID) will have 95% power to detect at least one of two such differences and 80% power to detect both differences.

#### 8.3.2 Complete Resolution of Pain in the Study Eye at Visit 5

Under the gatekeeping strategy, the power of each Family 2 (pain) hypothesis is limited by the power of the corresponding Family 1 (AC cells) hypothesis. However, the following statement shows that each Family 2 hypothesis is sufficiently powered in the event that the corresponding Family 1 hypothesis is rejected.

A two group  $\chi^2$  test with a 0.025 two-sided significance level will have 99% power to detect the difference between a LE gel 0.38% proportion,  $\pi_1$ , of 0.739 and a vehicle proportion,  $\pi_2$ , of 0.486 (odds ratio of 0.334) when the sample size in each group is 196.

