**Table 3: Bonferroni-based tree gatekeeping hypothesis structure**

Family	Null Hypothesis	Serial Rejection Set	Hypothesis Weight
F1	H 11 (TID AC Cells Resolution)	NA	1/2
	H 12 (BID AC Cells Resolution)	NA	1/2
F2	H 21 (TID Pain Resolution)	{ H 11 }	1/2
	H 22 (BID Pain Resolution)	{ H 12 }	1/2

95% confidence intervals will be constructed around the treatment differences using asymptotic normal approximations.

As a supportive analysis, these endpoints will be tested using the asymptotic Cochran Mantel-Haenszel statistic adjusting for site.

Supportive analyses of the primary analysis will be repeated on the per-protocol (PP) set.

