### 1.0 OCULAR SYMPTOMS

*The ocular symptoms of ocular pain, photophobia, itching, tearing, and ocular discharge are all to be graded by subjects using the following ordinal scales:*

**Ocular Pain:** *A positive sensation of the eye, including foreign body sensation, stabbing, throbbing, or aching.*

0 =	None:	Absence of positive sensation.
1 =	Minimal:	Presence of mild sensation or discomfort typical of postoperative ocular surgery (eg, diffuse or focal foreign body sensation, mild transient burning or stinging, etc.)
2 =	Mild:	Mild, tolerable aching of the eye.
3 =	Moderate:	Moderate aching sufficient to require the use of over the counter (OTC) acetaminophen.
4 =	Moderately Severe:	More prolonged aching requiring the use of an OTC analgesic other than acetaminophen.
5 =	Severe:	Intense ocular, periocular or radiating pain (eg, constant or nearly constant sharp stabbing pain, throbbing or aching, etc.) requiring prescription analgesics.

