##### Anterior Chamber Cells Assessment Method

- Standardly used slit lamp biomicroscope, magnification, and beam strength
- Aim at central cornea in pupillary axis
- Focus on anterior aqueous humor
- At plane of focus, perform first count of cells (do not focus on multiple planes)
- Move focus to central cornea
- Refocus on anterior aqueous humor
- At plane of focus, perform second count of cells
- Convert each cell count to a grade (See anterior chamber cells grading scale below)
- Record both grades and the average of both grades on the source documentation

**Cells:** Assess accumulation of white blood cells in anterior aqueous humor; pigmented cells and red blood cells are to be ignored.

0 = No cells seen

1 = 1 – 5 cells

2 = 6 – 15 cells

3 = 16 – 30 cells

4 = >30 cells

**Flare:** *Assess scattering of a slit lamp light beam when directed into the anterior chamber (Tyndall effect).*

0 =	None:	No Tyndall effect.
1 =	Mild:	Tyndall effect barely discernible.
2 =	Moderate:	Tyndall effect in anterior chamber is moderately intense. Iris pattern is seen clearly.
3 =	Severe:	Tyndall effect in anterior chamber is severely intense. Iris pattern cannot be seen clearly.
4 =	Very Severe:	Tyndall effect is very severely intense. The aqueous has a white and milky appearance.

**External Adnexa (Lids/Lashes):** *Assess erythema or edema of the external adnexa. In addition to erythema or edema, any other abnormality of the lid and lashes that is observed will also be noted and graded according to the same 4-point grading scale.*

0 =	Absent	No erythema or edema
1 =	Mild	Erythema or edema present in only 1 segment of the lid or lash
2 =	Moderate	Diffuse erythema or edema present all over the lid or lash; edema does not protrude over the gray line
3 =	Severe	Erythema injection is marked or edematous swelling extends anterior to the gray line and outside of palpebral fissure

**Ciliary Flush:** *Assess external congestion of blood vessels surrounding the limbus.*

0 =	Absent
1 =	Present

**Conjunctival Chemosis:** *Assess swelling of the conjunctiva.*

0 =	Absent	No edema
1 =	Mild	Edema present in 1 segment of the bulbar conjunctiva
2 =	Moderate	Diffuse and uniform edema present all over the bulbar conjunctiva, edema does not protrude over the gray line
3 =	Severe	Conjunctival swelling extends anterior to the gray line, outside of palpebral fissure

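### The primary Pearson tests are valid but leave the Visit 3 AC-cell and pain grades unused, which gives up a small gain in AC-cell power and pain precision

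*Combined protocol and SAP*

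**What the plan says.** Section 8.5.1.1 (Analysis of Primary Efficacy Endpoints) compares each active group with combined vehicle at Visit 5, and the comparison "will be tested using Pearson Chi-squared tests with p-values adjusted using a Bonferroni-based tree gatekeeping strategy". No baseline variable enters these tests. The one adjusted analysis named for the primary endpoints follows Table 3, as supportive: "these endpoints will be tested using the asymptotic Cochran Mantel-Haenszel statistic adjusting for site".

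Both baseline measures exist. At Visit 3, Section 6.1.3 lists "Perform a clinical assessment of ocular symptoms" and AC-cell grading ahead of randomization and the first in-clinic dose. Appendix B, 1.0 shows that pain is among those symptoms: "The ocular symptoms of ocular pain, photophobia, itching, tearing, and ocular discharge are all to be graded by subjects". Section 8.5.1 makes Visit 3 the baseline visit.

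Both grades can vary at entry. Inclusion criterion 12 asks for at least "Grade 2 anterior chamber (AC) cells (6-15 cells) in the study eye", so subjects start at Grade 2, 3 or 4. Sections 3.2.1.1 and 3.2.1.2 set no pain requirement at Visit 3. Sections 4.7.1 and 4.7.2 name no stratification of the randomization by either grade.

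Section 8.3.1 sizes the trial for the unadjusted test: a chi-squared test "with a 0.025 two-sided significance level will have 87% power to detect the difference" between 0.283 and 0.143 with 196 per group, with 95% power for at least one difference and 80% for both.

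**The concern.** When a baseline value of the outcome measure predicts the outcome, a test stratified by it usually has more power than an unadjusted test at the same sample size. Here that baseline is already recorded for both primary endpoints.

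The AC-cell tests are where power matters. Table 3 lets each pain hypothesis be rejected only after its AC-cell counterpart, and the stated power to show both AC-cell differences is 80%. A missed AC-cell test also loses the pain claim for that regimen.

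For pain the stake is precision and interpretation. A subject with Grade 0 pain at Visit 3 can count as a success at Visit 5, and the two groups may differ by chance in how many such subjects they hold. The baseline table in Section 8.5.2 names race, gender, age and iris color, but neither grade.

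**Working it through.** **Inputs from Section 8.3:** 196 per group; two-sided 0.025 per comparison (critical z 2.2414); AC cells 0.283 against 0.143; pain 0.739 against 0.486.

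**Step 1. Reproduce the plan's figures.** Power = Φ[(d − z·SE₀)/SE₁], with SE₀ from the pooled rate and SE₁ from the separate rates.

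- AC cells: d = 0.140, pooled rate 0.213. SE₀ = √(2 × 0.213 × 0.787/196) = 0.04136. SE₁ = √[(0.283 × 0.717 + 0.143 × 0.857)/196] = 0.04075. Φ[(0.140 − 2.2414 × 0.04136)/0.04075] = Φ(1.16) = 87.7% (plan: 87%).
- Pain: d = 0.253, SE₀ = 0.04921, SE₁ = 0.04752. Φ(3.00) = 99.9% (plan: 99%).
- Joint AC-cell power, 250,000 simulated trials with a shared vehicle group: 95.9% for at least one and 80.3% for both (plan: 95% and 80%).

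The plan's figures hold.

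**Step 2. Model for the gain.** The documents give neither the spread of Visit 3 grades nor their prognostic strength, so both are assumed. In each arm the odds of success fall by the same factor per grade, and the arm intercept is solved so that the overall rate stays at the planned value. The comparison is Pearson against a Cochran-Mantel-Haenszel (CMH) test stratified by grade, without continuity correction, in 200,000 simulated trials per scenario.

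**Step 3. AC cells, assumed 60/30/10% at Grades 2/3/4.** Example at factor 2: vehicle 0.180/0.099/0.052 (0.60 × 0.180 + 0.30 × 0.099 + 0.10 × 0.052 = 0.143); active 0.347/0.210/0.117. Pearson gives 88.1% per comparison and 80.3% for both differences.

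| Odds factor per grade | Stratified power, per comparison | Stratified power, both differences |
|---|---|---|
| 1 (not prognostic) | 87.9% | 80.0% |
| 1.5 | 88.3% | 80.6% |
| 2 | 88.8% | 81.3% |
| 3 | 89.8% | 82.8% |
| 4 | 90.4% | 83.8% |

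Variance ratios of 0.979 (factor 2) and 0.935 (factor 4) correspond to 196/0.979 = 200 and 196/0.935 = 210 subjects per group, that is 4 and 14 extra. With splits of 75/20/5% and 45/35/20%, stratified power runs from 87.8% to 91.6%.

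**Step 4. Pain, assumed 40/35/25% at Grade 0, 1, 2 or more.** Power is at least 99.8% with either test. The variance of the difference changes by +0.5, −2, −6, −14 and −20% for factors 1, 1.5, 2, 3 and 4. The unadjusted 95% half-width is 1.96 × 0.04752 = 9.3 points. It becomes 9.3 × √0.940 = 9.0 at factor 2 and 9.3 × √0.799 = 8.3 at factor 4.

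**Step 5. Chance imbalance at its 95% limit.** Shift = 1.96 × √(2/196 × between-stratum variance of the vehicle rates). At factor 4:

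- Pain (0.747/0.424/0.156): the between-stratum variance is 0.0558, so the shift is 1.96 × √(0.0102 × 0.0558) = 4.7 points.
- AC cells (0.205/0.061/0.016): the variance is 0.0059, so the shift is 1.5 points.

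Over factors 1.5 to 4 the shift is 1.6 to 4.7 points for pain, against 25.3 planned, and 0.6 to 1.5 points for AC cells, against 14.0.

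**Step 6. Type I error at nominal 0.025.** AC cells: stratified 0.0239-0.0256, Pearson 0.0245-0.0260. Pain: stratified 0.0243-0.0256, Pearson 0.0227-0.0236. The stratified test keeps its level.

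**The case against.** The case for leaving the plan alone is serious. Pearson is valid, pre-specified and matched to the sample size, and the gain rests wholly on assumptions. Up to factor 2 it is at most 0.7 points per comparison, less than the 1.1-point gap between the stated 87% and the simulated 88.1%. Eligibility cuts AC cells to Grades 2-4, which limits what the grade can explain. All of this stands, and it is why the point is small.

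The simulation uses exact grades, but Appendix B tells sites to "Record both grades and the average of both grades on the source documentation", so half-grades occur and banding loses some information. With an assumed 45/20/20/10/5% at 2, 2.5, 3, 3.5 and 4, stratifying on bands gives −0.2, +0.1, +0.5, +1.3 and +1.7 points for factors 1 to 4, against −0.1, +0.3, +0.8, +1.7 and +2.3 on exact grades. This also stands; the gain shrinks but remains for a prognostic grade.

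A 10% Grade 4 stratum holds about 20 subjects per group. For factors 2 to 4, that means 0.3-1.0 expected vehicle responders and 0.8-2.3 active ones. Sparse strata do not invalidate the CMH test, but they do call for a merging rule.

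For pain, no decision changes. The unadjusted standard error already allows for chance imbalance, so Step 5 shows the same variance reduction from another angle and should not be counted twice.

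Finally, the secondary change-from-baseline analysis does use the Visit 3 AC-cell grade, and Section 8.5.1.1 refers further secondary or exploratory analyses to a separate Statistical Analysis Plan whose text was not available. A supportive adjusted analysis may be there. The primary test, however, is fixed in Section 8.5.1.1.

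**Conclusion.** The point holds as a cheap improvement, not as a fault. The primary tests are valid and the stated powers reproduce, but two same-measure baselines go unused in them. For AC cells, stratifying is worth about −0.2 to +2.3 points of power per comparison under the 60/30/10% split, and up to 91.6% power under a wider one; power for both differences changes from 80.3% to between 80.0% and 83.8%. For pain the benefit is a more precise estimate only. These sizes depend on the assumed grade mix, on a common odds factor in both arms, and on stratifying by exact grade. If the grades do not predict outcome, nothing is gained and about 0.2 points of AC-cell power are lost.

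**What to change.** Before unmasking, amend Section 8.5.1.1 and its synopsis counterpart as follows.

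- Test H11 and H12 with a CMH test stratified by Visit 3 AC-cell grade, with strata set on the recorded average: 2 to <3, 3 to <4, and 4.
- Test H21 and H22 with a CMH test stratified by Visit 3 pain grade: 0, 1, and 2 or more.
- State the merging rule for sparse strata, based on counts pooled over treatment groups so that it can be applied while masked.
- Enter these p-values in the tree of Table 3 unchanged. Report Mantel-Haenszel risk differences with 95% confidence intervals, and keep the Pearson tests as supportive.
- Tabulate Visit 3 AC-cell and pain grades by group and, descriptively, show Visit 5 Grade 0 pain among subjects with pain of Grade 1 or more at Visit 3.

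If the sponsor prefers to keep Pearson as primary, the least change is to add the grade-stratified analysis as supportive, beside the site-adjusted one, with the same tables. That gives the precision and interpretation but not the AC-cell power.

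The cost is wording and code, since both grades are already collected. The downsides are the need for a merging rule, a primary test that differs from the one used for sizing, and the loss of about 0.2 points of AC-cell power if the grade is not prognostic.

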**Table 3: Bonferroni-based tree gatekeeping hypothesis structure**

Family	Null Hypothesis	Serial Rejection Set	Hypothesis Weight
F1	H 11 (TID AC Cells Resolution)	NA	1/2
	H 12 (BID AC Cells Resolution)	NA	1/2
F2	H 21 (TID Pain Resolution)	{ H 11 }	1/2
	H 22 (BID Pain Resolution)	{ H 12 }	1/2

95% confidence intervals will be constructed around the treatment differences using asymptotic normal approximations.

As a supportive analysis, these endpoints will be tested using the asymptotic Cochran Mantel-Haenszel statistic adjusting for site.

Supportive analyses of the primary analysis will be repeated on the per-protocol (PP) set.

### Analysis of Secondary Efficacy Endpoints

Analyses of secondary efficacy endpoints will be based on the ITT population. Missing data from subjects who are rescued or have discontinued the study prior to a study visit will be handled by either of two approaches: 1) missing data are imputed as failures; or 2) the last observation prior to the rescue medication or subject discontinuation is carried forward to subsequent visits (LOCF).

With the exception of change from baseline to each follow-up visit, each of the secondary efficacy endpoints will be independently tested at each visit using similar statistical methods employed for primary efficacy endpoints (without the p-value adjustments).

Change from baseline (Visit 3) in AC cells and flare composite score (Anterior Chamber Reaction), as well as individual cells and flare scores, will be analyzed using both continuous and discrete statistical methods by treatment and visit, with missing data imputed by LOCF.

Analysis of complete resolution of AC cells and Grade 0 pain at each visit will be conducted using a Pearson Chi-squared test, with missing data imputed as failures, and also with missing data imputed by LOCF. Similar analyses will be performed for complete resolution of AC cells and flare combined and for flare separately.

Other secondary or exploratory efficacy analyses may also be carried out as described in the study Statistical Analysis Plan.

### 8.5.1.2 Safety Endpoint Analyses

Safety endpoints will be summarized using discrete summary statistics by visit and treatment group.

Treatment-emergent AEs (TEAEs), defined as AEs that occur after the first dose of study medication, will be summarized prior to and after rescue medication and as ocular and non-ocular events separately. Ocular events will be summarized for treated eyes and fellow eyes separately. Non-treatment-emergent events will be presented only in the listings, with ocular and non-ocular events displayed separately.

A 95% confidence interval around the difference between treatment groups in the incidence of treatment-emergent AEs  $> 1\%$  will be constructed using asymptotic normal approximations.

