## 8.2 Hypotheses

The following multiple endpoints and multiple dose-vehicle comparison hypotheses will be tested using Bonferroni-based tree structured gatekeeping tests to control the overall type I error rate ( $\alpha = 0.05$ ) for the primary efficacy endpoints over the entire study. The hypotheses in Family 1 will be tested simultaneously. Each hypothesis in Family 2 will be eligible for rejection only if the corresponding hypothesis (TID, BID) in Family 1 is rejected.

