## 8.4 Study Populations

**Intent to Treat (ITT):** The ITT population will include all randomized subjects. Analysis on the ITT sample will be used as the primary efficacy analysis and will be performed for all efficacy endpoints. Subjects will be analyzed in the treatment group to which they were assigned.

**Per Protocol (PP):** The PP population will include all ITT subjects who remain in study through Visit 5 (Postoperative Day 8) and who have not deviated from the protocol in any way likely to seriously affect the primary outcome of the study. Important protocol deviations related to study inclusion or exclusion criteria, conduct of the trial, subject management, or subject assessment will be identified prior to locking the study database.

Analyses on the PP sample will be used as a supplement to the ITT analyses and will be performed for the primary efficacy endpoints. Subjects will be analyzed in the treatment group to which they were assigned.

**Safety:** The safety population will include all subjects who received at least 1 dose of study drug. All randomized subjects will be assumed to have taken study drug unless otherwise confirmed. If it is confirmed that a subject never took a dose of study drug, then the subject will be excluded from all safety analyses. All subjects in the safety population will be analyzed according to the treatment they actually received and not according to the treatment they were assigned to receive, in the event of discrepancy.

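### The planned normal-approximation 95% intervals for TEAE differences set the upper limit for excess risk too low too often when LE gel has several events and vehicle almost none (minor)

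*Combined protocol and SAP*

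**What the plan says.** Section 8.5.1.2 of the combined protocol and SAP, repeated in the Synopsis under Safety Endpoints, plans "A 95% confidence interval around the difference between treatment groups in the incidence of treatment-emergent AEs" above 1%. The interval "will be constructed using asymptotic normal approximations". Neither place gives a formula, a continuity correction, a score or exact method, or a rule for small or zero counts. Neither says which group the 1% rule refers to.

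Three other statements set the scale:

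- Section 8.3: "Each of the three treatment groups will consist of approximately 196 subjects".
- Section 8.4, on the safety population: "All randomized subjects will be assumed to have taken study drug unless otherwise confirmed". The safety denominators should therefore be close to the randomized numbers.
- Section 8.5.1: "Differences between treatment groups will be calculated as LE gel 0.38% minus vehicle". The upper limit is therefore the limit for excess risk on LE gel.

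**The concern.** One per cent of 196 is 1.96, so two events (2/196 = 1.02%) are enough to bring an event into the table if the rule is applied to a single group. The large-sample formula would then be used on counts such as 2 against 0. With no vehicle events, the vehicle group adds nothing to the plain variance: 0/196 is treated as a rate known to be exactly zero.

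A safety table is read for the largest excess risk still compatible with the data. A limit that is too short on that side understates possible harm, in the pattern where a new signal would appear (events on active, almost none on vehicle).

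**Working it through.** **Inputs.** From section 8.3: 588 subjects randomized 2:2:1:1 with the vehicle arms combined, so 588 × 2/6 = 196 per group. Assumed: safety denominators of 196, and the true TEAE rates, because the documents give none.

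**The plan's own figure.** The plan states no figure for the TEAE interval, so this step checks only the group size, through the AC-cell power (0.283 vs 0.143, two-sided 0.025, stated 87%). Power = Φ{[|p1 − p2|√n − z√(2·p̄·q̄)] / √(p1q1 + p2q2)}, with p̄ = 0.213 and z = 2.241. This gives Φ{[0.140 × 14 − 2.241 × 0.579] / 0.570} = Φ(1.16) = 0.877. The stated figure is reproduced.

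**One table by hand: 2 vs 0 events.**

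- Plain normal: d ± 1.96·√(p1q1/n + p2q2/n). Here d = 0.01020 and SE = √(0.01020 × 0.98980/196 + 0) = 0.00718. The interval is −0.39 to 2.43 points. Pooled variance gives the same upper limit, 2.43.
- Newcombe: upper = d + √[(u1 − p1)² + (p2 − l2)²]; lower = d − √[(p1 − l1)² + (u2 − p2)²]. The Wilson limits are 0.00280 to 0.03644 for 2/196 and 0 to 0.01922 for 0/196. Upper = 0.01020 + 0.02623 = 0.0364. Lower = 0.01020 − √(0.00740² + 0.01922²) = −0.0104. The interval is −1.04 to 3.64 points.

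| Events, LE vs vehicle | Plain normal | Newcombe | Gap at upper limit |
|---|---|---|---|
| 2 vs 0 | −0.39 to 2.43 | −1.04 to 3.64 | 1.22 |
| 3 vs 0 | −0.19 to 3.25 | −0.64 to 4.40 | 1.15 |
| 4 vs 0 | 0.06 to 4.02 | −0.25 to 5.13 | 1.11 |

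The gap narrows once vehicle has events: 0.93 at 2 vs 1, 0.74 at 2 vs 2, 0.50 at 10 vs 5.

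**Error rates.** A gap between two methods does not show which is wrong, so the upper-limit miss rate was enumerated exactly: the sum of b(x; 196, p1)·b(y; 196, p2) over displayed tables whose upper limit lies below p1 − p2, divided by the same sum over all displayed tables. The nominal value is 2.5%. The either-group rule displays a table if either count is at least 2. The pooled rule needs at least 4 events in 392, since 1% of 392 is 3.92.

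| True rate, LE vs vehicle | Normal, either-group rule | Newcombe, either-group rule | Normal, pooled rule |
|---|---|---|---|
| 3% vs 0.5% | 5.97% | 0.87% | 2.28% |
| 4% vs 0.5% | 5.92% | 1.66% | 3.99% |
| 5% vs 0.5% | 6.02% | 1.85% | 5.57% |
| 3% vs 1% | 4.32% | 1.85% | 3.93% |
| 2% vs 0.5% | 2.93% | 0.73% | not needed |
| 1.5% vs 0.5% | 2.97% | 0.53% | not needed |
| 1-2% vs 0.1% | 0.2-0.4% | 0.1% or less | not needed |
| 2% vs 2% | 2.26% | 1.79% | not needed |
| 5% vs 3% | 2.83% | 2.10% | not needed |

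The pattern has a simple cause. At 3% vs 0.5% the true difference is 2.5 points and the normal interval for 2 vs 0 stops at 2.43, so that table is a miss. At 2% vs 0.1% the true difference is 1.9 points and the same interval covers it.

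Two-sided coverage at 3% vs 0.5% is 100 − 5.97 − 0.72 = 93.3%, so the fault is mainly that the error sits on one side. If the rates are reversed (LE 0.5%, vehicle 3%), it moves to the lower limit, with 6.0% misses.

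**The case against.** **Newcombe is not the truth.** A reader might infer from the first table that the planned limit is a full point too low. The calculations do not support that: Newcombe's own upper-limit misses at the four main settings are 0.9-1.9%, below 2.5%, so part of the 1.1-1.2 point gap is its conservatism. This objection stands, and the point rests on the miss rates, not on the gap.

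**The fault is not general.** A reader might infer that every interval close to the 1% threshold is wrong. Counted over all possible tables, the normal upper limit does miss in 9.6% at 2% vs 0.1%, but that count includes tables with too few events to be displayed. Among displayed tables the excess disappears. The excess appears at LE rates of 3-5%, that is 196 × 0.03 = 5.9 to 196 × 0.05 = 9.8 expected LE events. Under the pooled rule it is absent at 3% vs 0.5%. This also stands and limits the scope.

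**The formula is inferred.** The text could cover other normal-based forms. At 2 vs 0, a continuity correction gives an upper limit of 2.94, the add-one adjusted (Agresti-Caffo) interval 2.98, and Miettinen-Nurminen, also an asymptotic method, 3.65. It cannot be said that every reading has this fault. But no adjustment is named, and a programmer would most naturally produce the plain interval.

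**Nothing depends on it.** Section 8.5.1.2 attaches no test of AE incidence and no decision to these intervals. That is correct and fixes the severity.

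**Conclusion.** The point holds as a minor one. Read naturally, the planned interval has an upper-limit error of about 4-6% instead of 2.5% when LE gel has several events and vehicle none or almost none. That is roughly twice nominal in the direction that understates excess risk. Elsewhere the error is near nominal, small or absent. The result assumes 196 per group, the plain normal formula, TEAE rates that the documents do not give, and display when either group has at least 2 events. Under the pooled rule the four main settings give 2.3%, 4.0%, 5.6% and 3.9%.

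A reader might infer that the primary efficacy intervals share the fault, because section 8.5.1.1 uses similar wording ("95% confidence intervals will be constructed around the treatment differences using asymptotic normal approximations"). They do not: at the planned rates the smallest expected count is 196 × 0.143 = 28. Nor do those intervals govern any claim, since the same section rejects hypotheses on multiplicity-adjusted p-values.

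**What to change.** In section 8.5.1.2 and in the Synopsis under Safety Endpoints, replace the asymptotic normal interval for TEAE differences with a named score-type interval, such as Newcombe's hybrid score interval without continuity correction. It would help, though it is optional, to state in the same sentence whether the 1% rule refers to either compared group, the LE group or the compared groups pooled.

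The change needs wording and a standard software option. Sample size, tests and conduct are unaffected. The cost is width: Newcombe intervals are 66% wider at 2 vs 0, 36% at 4 vs 0 and 12% at 8 vs 4. At 4 vs 0 the Newcombe interval includes zero (−0.25) although Pearson p = 0.044, whereas the plain interval does not (0.06). Miettinen-Nurminen avoids this (0.09) with practically the same upper limits in the zero-vehicle tables, but its lower-limit misses are 3.1% at 3% vs 0.5% and 4.5% at 3% vs 1%. Either is defensible if it is named in advance.
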